### **15.7. Coverage of Expenses**

The treated subjects will not be reimbursed or compensated for participating in the trial, however reimbursement for actual travel expenses related to study-required follow-up is allowed and will be stated clearly in the informed consent form when applicable.

### **15.8. Confidentiality**

Confidentiality of subjects will be maintained throughout the trial. A unique identification code will be assigned to each subject participating in this trial. Any data that may be published in abstracts, scientific journals, or presented at medical meetings will reference a unique subject code and will not reveal the subject's identity. The Sponsor and their CRO representative will make every reasonable effort to protect the confidentiality of the subjects participating in the trial.

## **16. Study Administration**

Cardiva Medical, Inc. will make necessary efforts to ensure that this study is conducted in compliance with GCPs and all applicable regulatory requirements.

### **16.1. Pre-Study Documentation Requirements**

Prior to shipment of investigational product, the following documents must be provided to Cardiva Medical, Inc.:

- Signed and dated Investigator Agreement and Financial Disclosure Form
- Fully executed Clinical Study Agreement and budget
- A copy of the written IRB approval of the protocol and Informed Consent Forms
- A copy of the IRB-approved Informed Consent Forms
- A copy of the curriculum vitae of the Principal Investigator.

### **16.2. Source Documentation**

The Principal Investigator must maintain detailed source documents on all trial subjects who are enrolled in the trial or who undergo screening. Source documents include subject medical records, hospital charts, clinic charts, Investigator's subject trial files, as well as the results of diagnostic tests (e.g., laboratory tests).

The following minimum information should be recorded in the subject's source records:

- The date the subject entered the study and the subject ID number
- The study name
- The date that informed consent was obtained
- Evidence that the subject meets trial eligibility requirements (e.g., medical history, trial procedures and/or evaluations)
- The dates of all trial related subject visits
- Evidence that required procedures and/or evaluations were completed
- Documentation of specific investigational devices used, if any
- Occurrence and status of any Adverse Events
- The date the subject exited the study, and a notation as to whether the subject completed the study or was discontinued, including the reason for discontinuation.

### **16.3. Record Retention & Custody**

The Investigator will maintain all essential trial documents and source documentation, in original format, that support the data collected on the study patients in compliance with the ICH/GCP guidelines. Documents must be retained for at least 5 years after the last approval of marketing application or until at least 5 years have elapsed since the formal discontinuation of the clinical investigation of the product. These documents will be retained for a longer period of time by

agreement with Cardiva Medical, Inc. or in compliance with other regulatory requirements. When these documents no longer need to be maintained, it is Cardiva Medical's responsibility to inform the Investigator. The Investigator will take measures to ensure that these essential documents are not accidentally damaged or destroyed. If for any reason the Investigator withdraws responsibility for maintaining these essential documents, custody must be transferred to an individual who will assume responsibility. Cardiva Medical, Inc. must receive written notification of this custodial change.

#### ***16.4. Criteria for Terminating Study***

Cardiva Medical, Inc. reserves the right to terminate the study but intends only to exercise this right for valid scientific or administrative reasons and reasons related to protection of patients. Investigators and associated IRBs will be notified in writing in the event of termination.

Possible reasons for study termination include:

- The discovery of an unexpected, significant, or unacceptable risk to the patients enrolled in the study.
- A decision on the part of Cardiva Medical, Inc. to suspend or discontinue development of the device.

#### ***16.5. Criteria for Suspending/Terminating a Study Center***

Cardiva Medical, Inc. reserves the right to stop the randomization of patients at a study center at any time after the study initiation visit if no patients have been enrolled or if the center has multiple or severe protocol violations without justification or fails to follow remedial actions.

Possible reasons for suspending/terminating a study center include:

- Repeated failure to complete electronic case report forms prior to scheduled monitoring visits.
- No or slow enrollment.
- Multiple or major protocol deviations without justification, or failure to follow remedial actions
- Failure to obtain written Informed Consent prior to enrollment
- Failure to report serious device-related AEs and/or UADEs to Cardiva Medical, Inc. within 24 hours of knowledge
- Loss of (or unaccounted for) investigational product inventory.

#### ***16.6. Investigator Responsibilities***

- Agree to sign and adhere to the Investigator Agreement
- Be willing to provide required assessments for analysis
- Be willing to perform and be capable of performing treatment procedures as outlined in this protocol and to delegate study responsibilities only to qualified personnel

- Comply with all required elements of this protocol and supply material suitable for quantitative analysis
- Agree to obtain written Informed Consent before any study specific procedures are performed
- Complete all electronic data modules prior to scheduled monitoring visits
- Be willing to change hospital routine if required by protocol, as long as patient safety and well-being is not compromised
- Adhere to all relevant Ultrasound Core Laboratory requirements as applicable.

## **17. Publication Policy**

The existence of this clinical trial is confidential, and it should not be discussed with persons outside of the trial. Additionally, the information in this document and regarding this trial contains trade secrets and commercially sensitive information that is confidential and may not be disclosed unless such disclosure is required by regional or national law or regulations. Subject to the foregoing, this information may be disclosed only to those persons involved in the trial who have a need to know, but all such persons must be instructed not to further disseminate this information to others. These restrictions of disclosure will apply equally to all future information provided that is indicated as confidential.

The data generated by this clinical trial are the property of the Sponsor, Cardiva Medical, Inc., and should not be disclosed without their prior written permission. These data may be used by the Sponsor now and in the future for presentation or publication at Sponsor's discretion or for submission to governmental regulatory agencies. The Principal Investigators may publish or present the trial results with prior consent of the Sponsor, but will not disclose confidential information. Prior to submission by a Principal Investigator for publication or presentation, the Sponsor will be provided with the opportunity to review the submission for confidential information and accuracy. The Sponsor will have the opportunity to a) approve the publication; b) require the removal of any Confidential Information (other than Study Data); and /or c) delay the proposed Publication for an additional ninety (90) days to enable Sponsor to seek patent protection.

The study will be posted on ClinicalTrials.gov prior to enrollment of the first subject, as required by regulation.

## **18. Regulatory Considerations**

### ***18.1. Role of Cardiva Medical***

As the Sponsor of this clinical study, Cardiva Medical has the overall responsibility for the conduct of the study, including assurance that the study meets the regulatory requirements of the Food and Drug Administration (FDA). In this study, Cardiva Medical will have certain direct responsibilities and will delegate other responsibilities to Consultants. Together, both Cardiva Medical and its Consultants will ensure adherence to the Sponsor's general duties (21 CFR 812.40),

selection of Investigators (21 CFR 812.43), monitoring (21 CFR 812.46), supplemental applications (21 CFR 812.35 (a) and (b)), maintaining records (21 CFR 812.140 (b)), and submitting reports (21 CFR 812.150 (b)).

### **18.2. General Duties [21 CFR 812. 40]**

The Sponsor's general duties consist of submitting the IDE application to FDA, obtaining FDA and IRB approvals prior to shipping the devices, selecting qualified Investigators and shipping devices only to those qualified Investigators. As the Sponsor, Cardiva Medical is also required to obtain signed study agreements, to provide the Investigators with the information necessary to conduct the study and adequate on-site training to conduct the trial, to ensure proper clinical site monitoring, and to provide the required reports to the Investigators, IRB's and FDA.

Cardiva Medical will be responsible for providing quality data that satisfies federal regulations and informing of serious unanticipated adverse events and deviations from the protocol. Written progress reports and a final report will be prepared and will coordinate with the Ultrasound Core Laboratory.

### **18.3. Monitoring [21 CFR 812. 46]**

The Sponsor and/or designee will conduct investigational site monitoring to ensure that all Investigators are in compliance with the protocol and the Investigators' agreements. The Sponsor and/or designee will monitor the sites to ensure that the completed Case Report Forms match the medical records, and resolve any differences. The Sponsor will retain the right to remove either the Investigator or the investigational site from the study.

The Sponsor will review significant new information, including unanticipated serious adverse events and ensure that such information is provided to the FDA, the Investigators and to all reviewing IRB's.

### **18.4. Supplemental Applications [21 CFR 812. 335 (A) and (B)]**

As appropriate, the Sponsor will submit changes in the Investigational Plan to the FDA and Investigators to obtain IRB re-approval.

### **18.5. Maintaining Records [21 CFR 812. 140 (B)]**

The Sponsor will maintain copies of correspondence, data, shipment of devices, serious adverse device effects and other records related to the clinical trial. The Sponsor will maintain records related to the signed Investigator Agreements.

### **18.6. Submitting Reports [21 CFR 812. 150 (B)]**

The Sponsor will submit the required FDA reports identified in this section of the regulation. This includes unanticipated serious adverse device effects, withdrawal of IRB or FDA approval, current 6-month Investigators list, annual progress reports, recall information, final reports, Investigators that use the device without obtaining informed consent, and significant risk device determinations.

**18.7. *Site Record Retention Policy [21 CFR 812. 140 (D)]***

The Sponsor, Ultrasound Core Lab, and clinical sites will maintain all records pertaining to this study for a period of five years following: the date on which the investigation is terminated or completed, or the date that the records are no longer required for purposes of supporting a pre-market approval application. Record retention dates will be provided to all concerned by the Sponsor.

**18.8. *Informed Consent & Institutional Review Board (IRB) [21 CFR Parts 50 & 56]***

All subjects must provide written informed consent in accordance with the local clinical site's IRB. A copy of the consent form from each center must be forwarded to the Sponsor for review and approval prior to submitting it to the IRB. Each site must provide the Sponsor with a copy of the clinical site's IRB approval letter and the informed consent. Yearly approvals for the continuation of the trial at each clinical site must also be forwarded to the Sponsor.

All Protected Health Information (PHI) to be collected in the study will be described in the informed consent form, and all study data will be managed in accordance with the Privacy Law (HIPAA).

## 19. Abbreviations and Definitions

### 19.1. Abbreviations

ACT	Activated clotting time
AE	Adverse Event
AV	Arteriovenous
CFR	Code of Federal Regulations
eCRF	Electronic Case Report Form
CV	Curriculum Vitae
DSMC	Data Safety Monitoring Committee
FDA	Food and Drug Administration
Fr	French
Hgb	Hemoglobin
Hct	Hematocrit
IDE	Investigational Device Exemption
IFU	Instructions for Use
INR	International Normalized Ratio
IRB	Institutional Review Board
LMWH	Low molecular weight heparin
PE	Pulmonary embolism
SAE	Serious Adverse Event
TPPT	Total Post-procedure Time
TTA	Time to Ambulation
TTH	Time to Hemostasis
TTCE	Time to Closure Eligibility
TTDE	Time to Eligibility for Discharge
TTD	Time to Hospital Discharge
UADE	Unanticipated Adverse Device Event

## **19.2. Definitions**

### **ACCESS SITE-RELATED HEMATOMA > 6 CM (minor safety endpoint)**

A localized collection of extravasated blood in subcutaneous tissue at the access site measuring > 6 cm at its widest point on visual inspection or palpation.

### **ACCESS SITE-RELATED BLEEDING REQUIRING TRANSFUSION (major safety endpoint)**

Bleeding originating from the venous access site(s), which has occurred to the degree that transfusion of blood products is necessary to maintain hemodynamic stability.

### **ACCESS SITE-RELATED BLEEDING REQUIRING > 30 MINUTES OF CONTINUAL MANUAL COMPRESSION TO ACHIEVE INITIAL VENOUS HEMOSTASIS (minor safety endpoint)**

Bleeding from the venous access site(s) requiring greater than 30 consecutive minutes of manual compression to achieve venous initial hemostasis.

### **ACCESS SITE-RELATED INFECTION CONFIRMED BY CULTURE AND SENSITIVITY: REQUIRING INTRAVENOUS ANTIBIOTICS AND/OR PROLONGED HOSPITALIZATION (major safety endpoint)**

Must meet at least one of the following criteria related to the venous access site(s): 1) positive wound culture requiring treatment with intravenous antibiotics; and/or 2) prolonged hospital discharge time directly related to complications of access site infection. Does not include administration of prophylactic antibiotic regimens.

### **ACCESS SITE-RELATED INFECTION CONFIRMED BY CULTURE AND SENSITIVITY: LOCALIZED AND REQUIRING INTRAMUSCULAR OR ORAL ANTIBIOTICS (minor safety endpoint)**

Must meet BOTH of the following criteria related to the venous access site(s): 1) positive wound culture requiring treatment with intramuscular or oral antibiotics; and 2) no prolongation of hospital discharge time directly related to complications of access site infection. Does not include administration of prophylactic antibiotic regimens.

### **ACCESS SITE-RELATED NERVE INJURY IN THE IPSILATERAL LIMB – NEW ONSET AND REQUIRING SURGICAL REPAIR (major safety endpoint)**

New onset access site closure-related nerve injury that requires surgical intervention to mitigate symptoms or prevent permanent nerve damage.

### **ACCESS SITE-RELATED NERVE INJURY – NEW ONSET AND PERMANENT (major safety endpoint)**

New onset access site closure-related nerve injury that persists for > 30 days and is deemed to be clinically significant by the Investigator.

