#### 7.4.4. Intra-Operative Randomization

At the end of the catheter-based procedure, with the procedural sheaths in place and under fluoroscopic visualization, an injection of contrast will be made to assess sheath placement and the anatomy of all venous access sites to verify the intra-operative eligibility criteria prior to randomization. These images should be saved and printed/stored with the subject's study records for monitoring purposes.

- Each venous access site must meet all intra-procedural access site-specific criteria for the subject to be eligible.

Once it has been determined that the subject does not meet any of the general intra-operative exclusion criteria, and that none of the venous access sites meet the specific access site exclusion criteria (i.e., all venous access sites must meet all study criteria for the subject to be eligible), then the subject is eligible for randomization.

- Once randomized, every access site will be closed according to the treatment assignment (i.e., either VVCS or manual compression).
- Study data will be captured for each access site, according to the instructions below.
- ***NOTE: Any subject that is randomized is considered to be enrolled, and all peri-procedural study data must be collected under the Intent to Treat principle regardless of deviations from the assigned treatment. For this reason, it is imperative that randomization is not performed until the case is complete and final eligibility criteria are confirmed.***
- ***If the subject is randomized to Mid-Bore VVCS and it is subsequently discovered that one or more of the access sites is not able to be closed (e.g., complication) apply manual compression to the affected access sites and close all eligible access sites using Mid-Bore VVCS. All study data will still be collected for each access site. See Section 4.2 Withdrawal of Subjects.***

At each investigational site, variable block randomizations will be performed separately by number of venotomy sites via EDC access at the conclusion of the index procedure, while the patient is on the table. Randomization will be stratified by 3 vs. 4 access sites, and there will be a 1:1 randomization ratio for Cardiva Mid-Bore VVCS vs. manual compression for access site closure. Refer to the Manual of Operations for instructions on how to randomize a subject.

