**Mid-Bore VVCS Treatment Arm Guidelines**

If the subject is randomized to receive the Mid-Bore VVCS, the device should be deployed according to procedure in the Instructions for Use (IFU) provided in **Attachment 3**. If protamine is administered, the Investigator may proceed immediately with sheath exchanges and VVCS deployment without re-checking the ACT to obtain a target value.

Document device information:

- Device Lot #
- Device Success evaluation
- Document any complications or device performance issues on the Device Performance eCRF; refer to the Manual of Operations for device return instructions in the case of any device performance issues.

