### **8.3. Primary Safety Endpoint**

On a **per-limb basis**, the rate of combined major venous access site closure-related complications through 30 days post-procedure, attributed directly to the closure method (i.e., “device-related” with no other likely attributable cause):

- Access site-related bleeding requiring transfusion;
- Vascular injury requiring surgical repair;
- Access site-related infection confirmed by culture and sensitivity, requiring intravenous antibiotics and/or extended hospitalization;
- New onset permanent access site-related nerve injury (i.e., persisting for > 30 days)
- New onset access site-related nerve injury in the ipsilateral lower extremity requiring surgical repair;
- Pulmonary embolism requiring surgical or endovascular intervention and/or resulting in death, to be confirmed by CT pulmonary angiography, lung ventilation/perfusion scan (VQ scan) or autopsy;
- Pulmonary embolism NOT requiring surgical or endovascular intervention and/or NOT resulting in death, to be confirmed by CT pulmonary angiography or lung ventilation/perfusion scan (VQ scan).

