## **14. Study Committee**

### **14.1. Data Safety Monitoring Committee (DSMC)**

An independent combination Clinical Events Committee (CEC) and Data Safety Monitoring Board (DSMB), referred to as the Data Safety Monitoring Committee, or DSMC, shall be responsible for systematic review and adjudication of all reported major and minor access site-closure related endpoint complications. All other events reported to be potentially device- or procedure-related by the Investigator will be reviewed by an independent Safety Manager and/or a member of the DSMC to determine whether it meets criteria for adjudication. In order to enhance objectivity and reduce the potential for bias, the DSMC members shall be independent of the Sponsor as well as the investigational sites/ Investigators.

Members shall consist of at least two (2) independent physicians with experience in catheter-based procedures, and a statistician. A third independent physician may be utilized in cases when disparity occurs between the two primary DSMC reviewers.

The methodology for performing these responsibilities shall be developed and outlined in the Adjudication Charter. Operational provisions shall be established to minimize potential bias.

The DSMC may recommend study termination if safety concerns warrant such action. The DSMC will establish guideline criteria for recommending study termination, to the extent that it is possible for the DSMC to predict adverse events or outcomes, before the proposed study begins.

The Safety Manager will maintain contact with the DSMC members to schedule event reviews in order to assure close and timely monitoring of adverse events and outcomes.

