**TRANSIENT ACCESS SITE-RELATED NERVE INJURY (minor safety endpoint)**

New onset access site closure-related nerve injury that persists for  $\leq$  30 days and is deemed to be clinically significant by the Investigator.

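### Sections 8.3 and 19.2 define permanent nerve injury, a primary safety component, differently, and 19.2 lets an Investigator who knows the closure method decide whether it counts

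*Combined protocol and SAP*

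**What the plan says.** Section 8.3, and the synopsis in the same terms, lists as a major complication "New onset permanent access site-related nerve injury (i.e., persisting for > 30 days". Duration is the only test.

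Section 19.2, under the heading for new-onset permanent nerve injury and labelled a major safety endpoint, counts an injury only if it lasts beyond 30 days and is also "deemed to be clinically significant by the Investigator". No criterion for significance is given, and no text says which of the two sections governs.

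Two neighbouring definitions in 19.2 matter here. The surgical-repair component has no significance condition: "New onset access site closure-related nerve injury that requires surgical intervention to mitigate symptoms or prevent permanent nerve damage". The transient (minor) definition is limited to injuries of 30 days or less and carries the same condition: the injury "is deemed to be clinically significant by the Investigator".

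Section 14.1 gives the independent DSMC "adjudication of all reported major and minor access site-closure related endpoint complications". It sends other events that the Investigator reports as potentially device- or procedure-related to a Safety Manager and/or a DSMC member for screening.

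No masking of the site team is described. Section 7.4.4 says "Once randomized, every access site will be closed according to the treatment assignment", and the VVCS guidelines in 7.4.5 say that after protamine "the Investigator may proceed immediately with sheath exchanges and VVCS deployment".

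**The concern.** The two sections define different sets of events for one component of the primary safety endpoint. Under 8.3, a mild sensory deficit still present after 30 days is a major event. Under 19.2 it is a major event only if the Investigator considers it clinically significant. If the answer is no, the event is not downgraded to minor, because the minor definition stops at 30 days. It leaves both composite rates.

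The person making that decision took part in or supervised the closure and knows the arm. The primary safety analysis is a non-inferiority test on a rare outcome. Leaving out VVCS events moves the result toward success, and the choice of definition should not rest on a judgement that knowledge of the arm could influence.

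**Working it through.** **Side by side: does an injury lasting more than 30 days count?**

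| Injury | Section 8.3 (major) | 19.2 permanent (major) | 19.2 transient (minor) |
|---|---|---|---|
| Investigator deems it significant | Yes | Yes | No (duration) |
| Investigator deems it not significant | Yes | No | No (duration and significance) |

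The second row is the conflict. If such an injury needed surgery it would still count under the surgical-repair component. Otherwise it is in neither rate.

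**Inputs for the size.** 204 subjects randomised 1:1 (section 4.2), so 102 patients and 204 limbs per arm. Assumed rate 2% per limb in both arms, margin 5 points, 2-sided 95% upper limit (sections 9.2.3 and 9.3). Section 9.3 describes the 204 per arm as patients; the stated power reproduces with 204 units per arm, which are limbs.

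**Plan's own figures first.** The Newcombe upper limit is U = (p1 − p2) + √[(u1 − p1)² + (p2 − l2)²], where u1 is the Wilson upper limit for VVCS and l2 the Wilson lower limit for compression.

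- 6 v 4 events: p1 = 0.0294, u1 = 0.0627, p2 = 0.0196, l2 = 0.0077. U = 0.0098 + √(0.0333² + 0.0120²) = 0.045, pass.
- 7 v 4 events: p1 = 0.0343, u1 = 0.0691. U = 0.0147 + √(0.0348² + 0.0120²) = 0.052, fail.

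This reproduces the 6/204 limit in 9.2.3. Exact enumeration over two binomials (n = 204, p = 0.02) gives power 0.877, against the stated 0.88.

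**Weight of one event.** 1/204 = 0.49 points. Expected events per arm: 0.02 × 204 = 4.1.

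**Planned analysis.** Patient-level bootstrap, one million resamples, 4 control events in different patients. It was run without the stratification by number of access sites.

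| VVCS events | VVCS patients with events in both limbs | Upper limit | Result |
|---|---|---|---|
| 7 | 0 | 0.044 | pass |
| 7 | 1 | 0.049 | pass |
| 7 | 2 | 0.054 | fail |
| 8 | 0 | 0.054 | fail |

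By either method one event separates pass from fail, but the position of the edge depends on the method and on clustering within patients.

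**How often a trial would sit on that edge.** Under Newcombe, the probability that removing exactly one VVCS event turns a fail into a pass is about 6% at true rates of 2% v 2%, and about 2% at 1% v 1%. That event must also be a persistent nerve injury judged not significant, so the joint chance is lower.

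**How many such injuries to expect.** Protocol Table 1 (RESPECT) shows permanent nerve injury in 0/275 VASCADE and 0/142 compression patients, and neuropathy not needing surgery in 1/275 and 0/142. These are arterial data. By the rule of three, zero counts are compatible with rates up to about 3/275 = 1.1% and 3/142 = 2.1%, or about 1 to 2 patients in 102. Assuming 0 to 2 affected limbs per arm, the shift in an arm's rate is 0 to 2/204 = 0.98 points.

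**Illustration of larger losses (assumed fractions).** With true rates of 7% v 2%, which is a difference at the margin, the Newcombe chance of declaring non-inferiority is 0.023 with no loss. It is 0.048 if 10% of VVCS events are lost and 0.096 if 20% are lost. If the same fractions are lost in both arms it is 0.040 and 0.067. The documents do not give the share of major events that would be nerve injuries, so nothing in them supports any particular fraction.

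**The case against.** A significance threshold is defensible. It keeps trivial residual numbness out of a composite called major, and 19.2 narrows other components too: transfusion must be needed for hemodynamic stability, and vascular injury must involve persistent bleeding. Section 19.2 can be read as the operational version of the short list in 8.3. This stands as an argument for having a threshold, and it is why simple deletion of the clause is not clearly right. It does not explain why the threshold is undefined or why an unmasked Investigator applies it. No other major component in 19.2 makes the Investigator's opinion of clinical significance a condition for counting.

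A reader might infer that this clause is the only opening for unmasked judgement. It is not. Section 8.3 restricts every component to events attributed to the closure method. Section 13.1 defines device-related as a judgement of the Investigator, and both routes to the DSMC in 14.1 depend on reporting. Removing the clause would leave that attribution route open.

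A reader might also infer that the DSMC is unable to count an injury the Investigator has dismissed. That follows from a literal reading of 19.2, but 14.1 leaves the methodology to an Adjudication Charter that is not among the documents. The charter may allow the DSMC to decide significance or may conceal the closure method. The documents do not say either way.

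Finally, excluded injuries are not invisible. Nerve complaints are asked of all subjects at discharge and at 30 days (7.4.6 and 7.5), and all reported adverse events are summarised by treatment (9.2.3). Those summaries do not enter the non-inferiority test. The clause in the minor definition affects only a rate that is not formally tested.

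**Conclusion.** The mismatch between 8.3 and 19.2 is real and should be reconciled before the endpoint is adjudicated. As written, 19.2 adds one avoidable route, besides device-related attribution, by which unmasked judgement can remove a primary safety event, and that event then falls outside the minor rate as well.

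The expected effect is small: 0 to 0.98 points in an arm's rate if 0 to 2 limbs are affected, with RESPECT suggesting the low end. It would decide the trial only if the result were already within one event of the limit. A reader might infer that the clause will favour VVCS; the documents give no basis for a direction or for an actual loss of events.

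The conclusion rests on three assumptions: that the Investigator knows the arm, which is inferred from who closes the sites and from the absence of any described masking; that the arterial RESPECT frequencies are a rough guide to venous access; and that the charter, which was not available, does not already settle the matter.

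**What to change.** Make 8.3 and 19.2 agree. In the 19.2 definitions of permanent and transient nerve injury, replace the Investigator's significance judgement with a determination by the independent DSMC, using records that do not show the closure method where feasible. If a significance threshold is kept, write its criterion into 19.2 and refer to it in 8.3, 8.4 and the synopsis.

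Send every new lower-extremity nerve complaint recorded at discharge and at the 30-day visit to the DSMC, for both significance and closure-relatedness. This also narrows the attribution route for this component. State in the Adjudication Charter that the DSMC's decision governs the endpoint.

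The cost is protocol and charter wording and a few more events to adjudicate. The complaints are already collected, so no new data collection is needed, and treatment is unchanged.
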